7.3.2 DF/HCC Expedited Reporting Guidelines

Investigative sites within DF/HCC and DF/PCC will report SAEs directly to the DFCI Office for Human Research Studies (OHRS) per the DFCI IRB reporting policy.

7.4 Expedited Reporting to Hospital Risk Management.

Participating investigators will report to the Risk Management office any participant safety reports or sentinel events that require reporting according to institutional policy.

7.5 Routine Adverse Event Reporting

All Adverse Events must be reported in routine study data submissions to the Overall PI on the

toxicity case report forms. AEs reported through expedited processes (e.g., reported to the IRB, FDA, etc.) must also be reported in routine study data submissions.

8. PHARMACEUTICAL INFORMATION

[figure not shown]
A list of the adverse events and potential risks associated with the investigational agent administered in this study can be found in Section 7.1.

8.1 Lenalidomide

8.1.1 **Description**

REVLIMID[®] (lenalidomide), a thalidomide analogue, is an immunomodulatory agent with anti-angiogenic properties. The chemical name is 3-(4-amino-1-oxo 1,3-dihydro - 2*H*-isoindol-2-yl) piperidine-2,6-dione and it has the following chemical structure:

1.1.1.1.1.1 Chemical Structure of Lenalidomide

3-(4-amino-1-oxo 1,3-dihydro-2H-isoindol-2-yl) piperidine-2,6-dione

The empirical formula for lenalidomide is $C_{13}H_{13}N_3O_{3}$, and the gram molecular weight is 259.3.

8.1.2 Form

Lenalidomide will be supplied as off-white capsules for oral administration. Capsule strengths are 2.5 mg, 5 mg, 10 mg, 15 mg, 20 mg and 25 mg. Lenalidomide will be shipped directly to patients or to the clinic site. Bottles will contain a sufficient number of capsules for one cycle of dosing.

8.1.3 Storage and Stability

Lenalidomide should be stored at room temperature away from direct sunlight and protected from excessive heat and cold.

8.1.4 **Compatibility**

Not applicable

8.1.5 Handling

- Females of childbearing potential should not handle or administer lenalidomide unless they are wearing gloves. Females of reproductive potential must adhere to the scheduled pregnancy testing as required in the Revlimid REMS® program.

8.1.6 Availability

Celgene Corporation will supply Revlimid[®] (lenalidomide) to study participants at no charge through Celgene's Revlimid Risk Evaluation and Mitigation Strategy[™] (REMS) (formerly known as RevAssist[®] Program). Lenalidomide will be provided in accordance with the Celgene Corporation's Revlimid REMS[®] program. Per standard Revlimid REMS[®] program requirements, all physicians who prescribe lenalidomide for research subjects enrolled into this trial, and all research subjects enrolled into this trial, must be registered in, and must comply with, all requirements of the Revlimid REMS[®] program.

8.1.7 Preparation

Lenalidomide will come pre-prepared by the manufacturer.

8.1.8 Administration

The subject will self-administer lenalidomide at home.

8.1.9 Ordering

Lenalidomide will be shipped on a per patient basis by the contract pharmacy to the patient. Only enough lenalidomide for one cycle of therapy will be supplied to the patient. Lenalidomide supplies are dispensed in individual bottles of capsules. Each bottle will identify the contents as study medication. In addition, the label will bear Celgene's name, quantity contained and the standard caution statement as follows: "Caution: New drug - Limited by Federal law to investigational use." Lenalidomide should not be handled by FCBP unless wearing gloves.

The study drug label must be clearly visible. Additional labels must not cover the Celgene label.

8.1.10 Accountability

The Investigator or designee is responsible for taking an inventory of each shipment of study drug received by the patient, and comparing it with the patient's drug diary. The Investigator or designee will verify the accuracy of the information on the drug diary, sign and date it, and retain a copy in the study file, and return a copy to Celgene or its representative upon request.

8.1.11 **Destruction and Return**

Patients will be instructed to return empty bottles or unused capsules to the clinic site. Celgene will instruct the Investigator on the return or destruction of unused study drug. If any study drug is lost or damaged, its disposition should be documented in the source documents. Study drug supplies will be retained at the clinical site pending instructions for disposition by Celgene.

9. BIOMARKER, CORRELATIVE, AND SPECIAL STUDIES

9.1 Biomarker Studies

BRAF is a human gene encoding a cellular growth signalling protein, which has been shown to be mutated in certain cancers including up to 50% of cases of LCH. The frequency of BRAF mutation in HS is unknown but appears to be minimal. The Trovagene cell free DNA (cfDNA) urine assay uses a proprietary method for extracting cell-free transrenal DNA from large volume urine samples and a PCR assay to amplify small DNA fragments while enriching for mutant alleles. These are then detected by droplet digital PCR (ddPCR).

This test was developed using urine samples from patients with stage IV / metastatic cancer. This test confirms the presence of a BRAF V600E mutation in urine DNA at levels of $\geq 0.03\%$ in comparison to the wild-type BRAF genes.

This is a laboratory developed test (LDT). This test was developed and its performance characteristics determined by Trovagene. It has not been cleared or approved by the FDA as clearance or approval of LDTs is not currently required.

Trovagene's laboratory is certified by the State of California LICENSE CLF 00338242 in compliance with CLIA (Clinical Laboratory Improvement Amendments) LICENSE 05D1094618, and is accredited by the College of American Pathologists LICENSE LAP 7190902.

- Optimal testing requires a 90-110ml urine sample
- No refrigeration necessary collect and ship at room temperature
- Collection kits will be provided by the manufacturer.

Plasma genotyping of cfDNA will be performed by the Belfer Institute blood biomarker lab using a validated ddPCR-based assay for the detection of BRAF V600E. Samples from venous blood draws will undergo centrifugation within 1 hour of sample collection and standard plasma collection (**Appendix C - SOP**). The plasma will then be transported directly to the Belfer Institute. Immediate extraction of cfDNA will then be performed on 2 mL of plasma using the QIAmp Circulating Nucleic Acid Kit (Qiagen) according to the manufacturer's protocol. DNA will then be eluted in 100 uL of AVE buffer and frozen at -80C until genotyping is performed. DNA quantification will be be performed using a fluorescence absorbence PicoGreen assay (Invitrogen).

Genotyping will subsequently be performed by ddPCR using standard reagents ordered from Bio-Rad. Allele specific probes for BRAF V600E will be used in participants. The design and optimization of these primers and the associated methodology has previously been described by our group (Oxnard et al., CCR, 2014).

Patients will undergo urine and plasma cfDNA testing at study entry. The results of this test will be compared with standard BRAF testing via immunohistochemistry and/or PCR on available tissue samples. If patients have a detectable BRAF mutation burden in cfDNA in the urine at study entry the test will be repeated at various timepoints as outlined in the study calendar (section 10). If the test is negative at baseline it will not be repeated. Results will be recorded in a quantitative fashion. This test may be performed in clinic (preferred) or taken home and shipped in a prepaid, addressed overnight mailer provided with the test kit.

9.2 Laboratory Correlative Studies

9.2.1 Serum TNF-alpha

- 9.2.1.1.1. Specimens will be collected in a DFCI clinical space (lab or infusion floor). One red top tube will be collected at specified timepoints. The test can be ordered via Lab Order Entry (LOE) in which a standard collection and processing workflow already exists.
- 9.2.1.1.2. The specimen will be frozen per standard DFCI lab procedure
- 9.2.1.1.3. Specimens are delivered via courier from DFCI lab control to the Mayo Clinic Laboratory three times daily
- 9.2.1.1.4. Collection of the specimen will occur at DFCI. The assay will be run at the Mayo Clinic Laboratory per current standard procedure.

10. STUDY CALENDAR

Baseline evaluations are to be conducted within 1 week prior to start of protocol therapy. Scans and x-rays must be done \leq 4 weeks prior to the start of therapy. In the event that the participant's condition is deteriorating, laboratory evaluations should be repeated within 48 hours prior to initiation of the next cycle of therapy.

Assessments must be performed prior to administration of any study agent. Study assessments and agents should be administered within \pm 3 days of the protocol-specified date, unless otherwise noted.

	Pre- Study	C1 D1	C1 D15	C2 D1	C2 D15	C3 D1	C3 D15	C4 D1	C5 D1	C6 D1	C7 D1	C8 D1	C9 D1	C10 & 11 D1	C12 D1	Off Treatment ^l	Follow Up ^m
Lenalidomide		Х	Х	Х	Х	Х	Х	Х	Х	Х	Х	Х	Х	Х	Х		
Anticoagulation		Х	Х	Х	Х	Х	Х	Х	Х	Х	Х	Х	Х	Х	Х	X ^h	
Informed consent	Х																
Demographics	Х																
Medical history	Х																
Concurrent meds			Х														X
Physical exam	Х	Х	Х	Х		Х		Х		Х		Х	Х		Х	Х	Х
Vital signs ^a	Х	Х	Х	Х		Х		Х		Х		Х	Х		Х	Х	Х
Height	Х	Х	Х	Х		Х		Х		Х		Х	Х		Х		Х
Weight	Х	Х	Х	Х		Х		Х		Х		Х	Х		Х	Х	Х
Performance status	Х	Х		Х		Х		Х		Х		Х	Х		Х	Х	Х
CBC w/diff, plts	Х	$\mathbf{X}^{\mathbf{j}}$	Х	\mathbf{X}^{j}	X^k	Х	X^k	Х		Х		Х	Х		Х	Х	Х
Serum chemistry ^b	Х	Х	Х	Х	X^k	Х	X^k	Х		Х		Х	Х		Х	Х	Х
EKG	Х																
Bone marrow biopsy	\mathbf{X}^{i}																\mathbf{X}^{i}
Adverse event evaluation			Х														X
Tumor measurements ^c	Х					Х				Х			Х		Х	Х	Х
Radiologic evaluation ^d	Х					Х				х			Х		Х	х	Х
B-HCG ^e	X ^b	Х		Х		Х		Х		Х		Х	Х		Х		Х
Urine/ Plasma Assay for BRAF mutation ^f	Xe					Х				х					Х	Х	Х
Serum TNF-alpha ^g	Х					Х				X					Х	Х	Х

a: Temperature, BP, HR and O2 saturation by pulse oximetry at rest.

b: Albumin, alkaline phosphatase, total bilirubin, bicarbonate, BUN, calcium, chloride, creatinine, glucose, potassium, total protein, SGOT [AST], SGPT [ALT], sodium.

c: Tumor measurements are repeated at C3D1, C6D1, C9D1 and C12D1 and then every 3 months thereafter until month 24. After month 24 tumor assessments will occur every 6 months (+/- 2 weeks) until month 36 from treatment initiation. Documentation (preferably radiologic) must be provided for participants removed from study for progressive disease. A window of +/- 1 week is allowed prior to month 24 but tumor assessments must occur prior to dosing on the relevant cycle when active treatment is being administered

- d: MRI of the brain is required for all patients but only needs to be repeated at follow-up if abnormal at baseline; PET/CT from scalp to toes is preferred for all patients but if PET/CT is not covered by insurance CT of chest, abdomen and pelvis as well as bone scan is an acceptable alternative; the same imaging modality should be used at each response time point. Radiologic measurements should be performed on C3D1, C6D1, C9D1, and C12D1 and then every 3 months thereafter until month 24. After month 24 tumor assessments will occur every 6 months (+/- 2 weeks) until month 36 from treatment initiation. A window of +/- 1 week is allowed prior to month 24 but tumor assessments must occur prior to dosing on the relevant cycle when active treatment is being administered.
- e: Serum pregnancy test [women of childbearing potential defined as a sexually mature female who 1) has not undergone a hysterectomy or bilateral oopherectomy; or 2) has not been naturally menopausal for at least 24 consecutive months]. WCBP must have a pregnancy test prior to each cycle. This will be performed in clinic when there is an evaluation on day 1 of any cycle scheduled. Pregnancy testing will occur per the REMS program when a patient is not scheduled for clinic evaluation on day 1 of any cycle.
- f: Urine/serum assay will only be repeated at the time points indicated if abnormal at baseline. Urine assay for BRAF mutation has a +/- 7 day window. Serum assay has a +/- 3 day window.

g: Samples can be drawn pre or post dose at the time points indicated, they are not dependent on dosing.

h: If patient did not experience a venous thromboembolic event and there is no other clinical indication for anticoagulation then per protocol anticoagulation can be discontinued at this juncture. If there is separate clinical indication for anticoagulation, including a thromboembolic event while on protocol, the nature and duration of anticoagulation should be determined as clinically indicated by standard of care and the discretion of the treating physician.

i: Only required if at least one unexplained cytopenia of grade 2 or greater is present at baseline or if PET/CT suggests bone marrow involvement; only needs to be repeated if abnormal at baseline.

- j:
- CBC with automated differential will be checked every 7 days (+/- 1 day) during cycles 1 and 2; local labs are acceptable. Labs only necessary if dose escalation occurs. Note, these labs can be obtained at a local laboratory. Window for labs is +/- 3 days. k:
- Window for end of treatment visit is +/-7 days from the date of last dose. 1:
- The first follow up visit will occur 3 months from the date of last dose and then every 3 months thereafter. Window for follow up visits is m: +/- 2 weeks.

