1.3 Secondary Objectives

- To define the progression free survival (PFS) after treatment with lenalidomide
- To define the overall survival (OS) after treatment with lenalidomide
- To describe the safety profile of lenalidomide in LCH, ECD, and HS
- To assess quantitative changes in urinary and plasma cell free DNA harboring the BRAF V600E mutation and correlate the presence or absence of the BRAF V600E mutation with response
- To assess serial changes in TNF-alpha levels in patients treated with lenalidomide
- To assess the mutational landscape of these diseases using Oncopanel

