TNF-alpha is thought to promote the proliferation and survival of dendritic cells and histiocytes and thalidomide inhibits TNF-alpha production by affecting the gene promoter as well as other anti-cytokine effects (19). Thalidomide has reported activity in histiocyte disorders, including HS and LCH. Thalidomide has several drawbacks, including the common side effects of neuropathy and somnolence. Lenalidomide is potentially a more potent TNF-alpha inhibitor and does not cause neuropathy, making it potentially a more useful agent for prolonged administration. There are case reports describing the activity of lenalidomide in a variety of histiocyte disorders (20, 21). There is also emerging evidence on the important role of activation of RAS-PI3K-AKT signaling in histiocyte disorders and the AKT inhibitor afuresertib has been studied in LCH patients (22, 23). Lenalidomide potentially has inhibitory effects on AKT as well (24). We therefore planned a broader study to more systematically evaluate the efficacy of lenalidomide and describe the toxicity of lenalidomide in a population of patients with LCH and HS. Given the putative mechanism of action we seek to correlate serum TNF-alpha levels with response. In patients with a known BRAF V600E mutation we also wish to explore the possibility of using BRAF mutation burden assessed in urine and plasma cell free DNA as a biomarker of disease activity.

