The mechanism of action of lenalidomide remains to be fully characterized. Lenalidomide possesses immunomodulatory and antiangiogenic properties. Lenalidomide inhibited the secretion of pro-inflammatory cytokines and increased the secretion of anti-inflammatory cytokines from peripheral blood mononuclear cells. Lenalidomide inhibited cell proliferation with varying effectiveness (IC50s) in some but not all cell lines. Of cell lines tested, lenalidomide was effective in inhibiting growth of Namalwa cells (a human B cell lymphoma cell line with a deletion of one chromosome 5) but was much less effective in inhibiting growth

of KG-1 cells (human myeloblastic cell line, also with a deletion of one chromosome 5) and other cell lines without chromosome 5 deletions. Lenalidomide inhibited the expression of cyclooxygenase-2 (COX-2) but not COX-1 in vitro.

Pharmacokinetics and Drug Metabolism

Absorption:

Lenalidomide, in healthy volunteers, is rapidly absorbed following oral administration with maximum plasma concentrations occurring between 0.625 and 1.5 hours post-dose. Co-administration with food does not alter the extent of absorption (AUC) but does reduce the maximal plasma concentration (Cmax) by 36%. The pharmacokinetic disposition of lenalidomide is linear. Cmax and AUC increase proportionately with increases in dose. Multiple dosing at the recommended dose-regimen does not result in drug accumulation.

Pharmacokinetic analyses were performed on 15 multiple myeloma patients treated in the phase I studies. Absorption was found to be rapid on both Day 1 and Day 28 with time to maximum blood levels ranging from 0.7 to 2.0 hours at all dose levels (5mg, 10mg, 25mg, and 50mg). No plasma accumulation was observed with multiple daily dosing. Plasma lenalidomide declined in a monophasic manner with elimination half-life ranging from 2.8 to 6.1 hours on both Day 1 and 28 at all 4 doses. Peak and overall plasma concentrations were dose proportional over the dosing range of 5mg to 50mg. Exposure (AUC) in multiple myeloma patients is 57% higher than in healthy male volunteers.

Pharmacokinetic Parameters

Distribution

In vitro (¹⁴C)-lenalidomide binding to plasma proteins is approximately 30%.

Metabolism and Excretion

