Patients who have a detectable BRAF V600E mutation in the urine and/or plasma at baseline will have serial measurements every 2 months for 12 months or until protocol discontinuation (whichever occurs sooner). Note, if patients have a positive urine or serum BRAF assay both tests will repeated at all of the aforementioned timepoints. The results of urine and ddPCR-based plasma genotyping will be compared to tissue genotyping for BRAF V600E.

In a descriptive fashion we will investigate whether serum TNF- α levels, ddPCR for BRAF and/or urine cell free DNA harboring the BRAF V600E serves as a biomarker for response.

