13. STATISTICAL CONSIDERATIONS

13.1 Study Design/Endpoints

The primary endpoint of this study is to evaluate the overall response rate of lenalidomide in patients with LCH. This is a pilot study with a planned accrual of 12 patients. A small sample size was selected due to the rarity of the disease and the difficulty in accruing a larger number of patients at a single center.

Study treatment will be considered worthy of further evaluation if at least three (25%) of 12 patients experience a response. The 90% exact binomial confidence limits for three responses in 12 patients is 7-53%. We will consider a response rate of 5% unworthy of further study for this patient population, and note that two responses in 12 patients is the maximum number of responses which still includes the unworthy response rate of 5% in its confidence limits.

The limited sample size may cause us to miss a small but potentially clinically meaningful response rate or to overestimate the response rate. We are willing to accept this in order to complete the trial in a reasonable time period while recognizing that the results of this trial will be used to determine whether a larger phase II trial of lenalidomide is warranted in which case such a trial would be proposed to the Histiocytosis Society.

Secondary endpoints will include:

- Duration of response
- Progression free survival

- Overall survival
- Description of toxicity
- Quantitative serial measurements of urine and plasma cell free DNA for BRAF mutation as a biomarker of response
- Quantitative serial measurements of serum TNF-alpha levels as a biomarker of response

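### Footnote g lets Day 1 TNF-alpha samples be drawn before or after the dose, so the series may mix drug-free and recently dosed values; fix the draw as pre-dose and record times

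*Combined protocol and SAP*

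**What the plan says.** Section 1.3 lists as a secondary objective: "To assess serial changes in TNF-alpha levels in patients treated with lenalidomide". Section 13.1 gives the endpoint as "Quantitative serial measurements of serum TNF-alpha levels as a biomarker of response", and Section 13.6 repeats it without a test or a decision rule. Section 2.4 describes the analysis as exploratory: "In a descriptive fashion we will investigate whether serum TNF- α levels", along with the BRAF cell-free DNA assays, can serve as a marker of response.

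The reason for choosing this marker is in Section 2.1: "Lenalidomide is potentially a more potent TNF-alpha inhibitor and does not cause neuropathy", and then "Given the putative mechanism of action we seek to correlate serum TNF-alpha levels with response".

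The calendar in Section 10 marks TNF-alpha at pre-study, C3D1, C6D1, C12D1, Off Treatment and Follow Up. None is marked at a Day 15 visit. Two statements in that section govern when the tube is drawn:

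- The general rule above the table: "Assessments must be performed prior to administration of any study agent", with a window of 3 days either side.
- Footnote g, attached to the TNF-alpha row only: "Samples can be drawn pre or post dose at the time points indicated, they are not dependent on dosing".

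Section 5.1 sets dosing on days 1-21 of each 28-day cycle. Section 2.2 reports, for myeloma patients, an "elimination half-life ranging from 2.8 to 6.1 hours on both Day 1 and 28 at all 4 doses", with no accumulation on daily dosing and peak levels at 0.7 to 2.0 h.

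**The concern.** The protocol measures TNF-alpha because it expects the drug to lower it, yet footnote g treats the time since the last capsule as irrelevant. No evidence is given for that.

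The baseline sample is free of lenalidomide: it precedes treatment, and prior lenalidomide is an exclusion (3.2.3). A later Day 1 sample may be equally drug-free, or may follow a capsule by an hour or two. If the choice varies from visit to visit or patient to patient, part of any apparent rise or fall may reflect clinic logistics rather than disease or a lasting drug effect. With three scheduled on-treatment points and 12 planned patients, such variation will not reliably average out, and describing the data without a formal test does not remove it.

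At stake is the reading of one secondary biomarker endpoint. The response-rate endpoint and the 3-of-12 criterion are untouched.

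**Working it through.** The plan gives no TNF-alpha standard deviation, effect size or kinetics, so there is no planned figure to reproduce. What can be checked is the drug exposure behind each permitted draw.

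**Inputs.** Last scheduled dose on Day 21 and next dose on Day 29, which is Day 1 of the next cycle (Section 5.1). Half-life 2.8 to 6.1 h (Section 2.2). Window of 3 days either side (Section 10). Fraction of drug remaining = 2^(-gap / half-life).

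**Pre-dose draw on Day 1.** Days 22-28 carry no dose. The gap from the Day 21 dose is 8 days × 24 h = 192 h.

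- 192 / 6.1 = 31.5 half-lives; fraction remaining about 3 × 10^-10.
- 192 / 2.8 = 68.6 half-lives; fraction remaining smaller still.

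**Draw 3 days early.** The gap is 5 × 24 = 120 h.

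- 120 / 6.1 = 19.7 half-lives; fraction remaining about 1.2 × 10^-6.
- 120 / 2.8 = 42.9 half-lives.

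**Sensitivity to the half-life.** The figures come from myeloma patients, and this trial admits patients with creatinine clearance down to 30. For 192 h to be as few as 5 half-lives (2^-5 = 3% remaining), the half-life would have to be 192 / 5 = 38.4 h, about 6.3 times the upper figure (38.4 / 6.1). A pre-dose draw is drug-free in plasma under any half-life near those stated.

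**Post-dose draw.** It may fall near the peak. By simple decay from the time of the dose, ignoring absorption, the fraction of that dose remaining is 61-80% at 2 h and 5-26% at 12 h. If the cycle starts on time and the visit falls 3 days late, the draw on Day 4 can follow up to four doses.

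**Off Treatment draw.** Footnote l allows 7 days either side of the last dose, so this sample can also be on or off drug.

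**Reading the rules together.** The general rule puts assessments before study agent; footnote g releases TNF-alpha from it. Footnotes c and d require tumour measurements and imaging to precede dosing at C3, C6 and C12, so the same visits are already arranged around a pre-dose assessment. Section 5.1 requires a diary of each dose, but nothing requires the TNF-alpha draw time to be recorded against it.

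Section 2.4 promises sampling every 2 months, whereas C3D1, C6D1 and C12D1 fall 56, 140 and 308 days after C1D1. These schedules need reconciling, but the timing question arises under either.

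**The case against.** A reader might infer that Day 1 sampling cannot show the change under lenalidomide that the objective asks for. The documents do not support that. The objective is serial change over treatment and a descriptive link to response; no passage sets an acute, on-dose aim. The three Day 1 draws coincide with tumour assessment, which suits a response marker, and a lasting fall with disease control could show against baseline. This part of the objection stands: the Day 1 schedule itself is acceptable.

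Plasma half-lives also describe the drug, not TNF-alpha. Section 2.1 attributes the thalidomide effect to inhibited production through the gene promoter, and Section 2.2 says the mechanism of lenalidomide is not fully characterised. Nothing states that TNF-alpha moves within hours of a capsule or recovers within the drug-free week. This stands too, and it leaves the size of the problem unknown.

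Footnote g can fairly be read as a specific exception to the general rule rather than a contradiction of it, and mixing is permitted, not certain: a site could draw every sample pre-dose. Both points are right. But an exception that expressly allows either timing gives no assurance of consistency. The diary would allow sorting afterwards only if draw times were kept, which the plan does not require.

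Finally, one might ask for an on-drug sample at C1D15, where blood is already drawn. That would serve an aim the protocol does not state. It would reflect only the cycle 1 dose and fall in the period when Section 7.1 places most tumour flare, which Section 6 allows to be treated with NSAIDs or corticosteroids. It is not a necessary change.

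**Conclusion.** The point holds as an avoidable source of variation in a secondary, descriptive endpoint. Footnote g permits Day 1 TNF-alpha values from two exposure states: drug-free in plasma (192 h, 31 to 69 half-lives after the last scheduled dose) and recently dosed. It gives no means of telling them apart. Within at most 12 patients this can confound drug exposure with change over time.

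The exposure contrast rests on the half-lives in Section 2.2 and on dosing to schedule. Its effect on TNF-alpha depends on an unknown. If suppression lasts hours to a few days after a dose, mixed timing could distort the series materially; if it outlasts the 8-day gap, the harm is smaller. Neither case argues for leaving the timing open. The documents do not support saying that the series is uninformative or that mixing will certainly occur. The change is worth making because it is nearly free.

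**What to change.** Replace footnote g with wording such as: *Day 1 TNF-alpha samples are drawn before the first dose of that cycle; record the draw time and the date and time of the last lenalidomide dose for every sample, including Off Treatment.* This also brings the row into line with the general calendar rule.

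In Section 13.6, state that pre-dose Day 1 values are compared with the drug-free baseline as the response-biomarker series. Any sample found to have been drawn after a dose should be flagged and shown separately, and Off Treatment values listed with time since last dose.

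The cost is one footnote, a sentence or two in Section 13.6 and the added time fields on the case report form. No extra visit, tube or assay is needed. The patient takes the Day 1 capsule after the draw, and the late side of the 3-day window can be used for this sample only if the start of the cycle moves with it. A C1D15 sample is optional; if taken, it should be labelled as reflecting the cycle 1 dose only and as open to influence from tumour flare and its treatment.
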